Pain: We recommend the VAS. The VAS appears in most studies of low back pain and has specifically been recommended²⁹. Mannion et al also suggest that most patients treat the VRS and NRS as a VAS by simplifying each respective numerical scale to approximate that seen in the VAS. When the scale is properly explained, it has been shown to be reproducible and easy to interpret³⁵. However, this choice may be considered arbitrary as studies measuring the variance between various numerical scales suggest any numerical scale may be used with expected reproducible results³⁵. One advantage of using the NRS is that the Minimally Clinically Important Difference (MCID) has already been calculated as 2^{35,38}. With respect to expected outcomes, Farrar suggests that a relative treatment difference in pain level of 33-50% on any scale is considered clinically meaningful⁴⁰.

Function: We recommend the Roland-Morris Disability Questionnaire. While both the ODI and RMDQ are reliable, valid, and require only 5 minutes to complete, the RMDQ is the most studied of all functional outcome assessments³⁵. Published Mean Detectable Change (MDC) is available for both of these studies though it varies from study to study, based on the initial measured level of function. Generally, a low initial score indicates that less than a 5 point difference is needed to identify a detectable change. Higher baseline scores may necessitate as much as a 8-9 point difference to identify a change. Roughly, a 5 point difference correlates to a 20% change on the scale³⁵. Other authors such as Bombardier et al suggest that a 2-3 point difference is a MCID⁴¹.

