Patient Selection: It has been noted that the natural course of acute low back pain is such that rapid improvement of pain, disability, and return to work is experienced in the majority of patients by 4 weeks⁵⁶. Further improvement is then noted up to 3 months^{55,56}. Of the patients who go on to develop chronic low back pain, 90% endorse stable pain and disability⁵⁵. Kovacs et al note that the extent to which disability can be attributed to pain itself (vs psychosocial and cognitive measures) is highest in the acute setting (pain <14 days)⁵³. Disability from chronic low back pain (pain >12 weeks in duration³³) is also influenced by multiple factors to include both pain itself and psychosocial factors⁴². Despite this finding, attempts to address the psychosocial aspects with antidepressants have inconsistently shown true benefit^{58,60}. Even though chronic low back pain is a multidimensional problem, authors such as Kovacs et al agree that the enduring presence of pain can predict disability, and disability in turn may predict quality of life. Treatment plans for patients with chronic low back pain encompass a variety of treatments from advice/continued activity to pain medications to use of complementary and alternative medicine^{43-46,49,54}. Yet despite this multifaceted approach, a substantial number patients continue to experience pain and disability, albeit at a stable level^{55,56}. Because of this stability, patients with chronic low back pain would be ideal study population to assess the impact of MSM on low back pain.

MSM has not been well studied in low back pain. Tant et al report that it may be helpful in the treatment of chronic low back pain⁵⁷ when coupled with glucosamine complex. However, their study used a small number of patients and did not include a true placebo control for glucosamine/MSM. Further information on MSM and chronic low back pain is otherwise lacking.

Adverse Side Effects: As noted above, Kim et al¹³ reported adverse side effects of bloating, constipation, indigestion, fatigue, decreased concentration, insomnia and headache, though these symptoms were not any more prevalent in the group taking MSM than the placebo group.

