Proposal of Materials and Methods: Selection of proper follow up time has been based on studies of MSM in osteoarthritis. Follow up time ranges from 2¹³ to 12 weeks¹². In the study by Kim et al¹³, efficacy was not noted until 4 weeks into the study. This improvement was even more notable at 8 and 12 weeks than at 4 suggesting that improvement in symptoms may require longer exposure MSM. For this reason, the impact MSM on low back pain, function and quality of life should be carried out to at least 12 weeks.

The use of 4 week intervals for reassessment mirrors the protocol by Kim et al. This is convenient considering the PIQ-6/R was designed for a 1 (acute) or 4 week (chronic) follow up.

Inclusion and Exclusion Criteria for this study will be similar to the common criteria from various studies on Low Back Pain^{42-44,52,55,58,61}.

Studies of MSM and osteoarthritis have recommended MSM dosing ranging from 500mg TID to 3 g BID^{12,13}. Doses of 6 g daily are considered safe^{13,24}. As noted above, studies in rats found that doses 5-7 times the maximum recommended daily amount may be given without any appreciable toxicity^{15,68}. Human studies using >6gm/day have not been performed. MSM will be given in the dose of 1500mg x2 Tabs, BID. Standard of care naproxen is typically defined as a dose of 225-550 mgs twice a day although it may vary depending on the provider.

3.5.1. Bibliography:

3. Teets RY, Dahmer S, Scott E. Integrative Medicine Approach to Chronic Pain.
5. Ernst E. Prevalence of use of complementary/alternative medicine: a systematic review. *Bull World Health Organ [online].* 2000; 78(2) 258-266

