- Subjects will be asked “On a scale of 0-10, with 10 being the worst pain, what is your current level of pain”.
- Research staff will record whether subject had any side effects to report.
- Subjects will have their study medications refilled.
- Research staff will collect the subject’s Study Diary, issue them a new one, and remind them to bring it with them to the next study visit.
- Research staff will remind subjects to take the pills as instructed and to return the bottle to the research staff at the next visit.
- Subjects will have the following research-driven blood test drawn via 1 venipuncture (5-10 mls, approximately 1-2 teaspoons of blood drawn for each test) which include:
 - Comprehensive metabolic panel (liver function, renal function, plasma glucose tests).
**Subjects who have had a comprehensive metabolic panel test within the one week prior to this visit will not need to have this test repeated unless they are abnormal.*
 - Complete Blood Count.
**Subjects who have had a complete blood count test within the one week prior to this visit will not need to have this test repeated unless they are abnormal.*

Visit 4/Week 12 *SUBJECTS STOP TAKING STUDY PILLS AT THIS VISIT:

- Record: Weight (in pounds), blood pressure, history of lower back surgeries, medical history, and concomitant medications.
- Subjects will be asked to complete the following questionnaires:
 - RMDQ
 - PIQ-6
- Subjects will be asked “On a scale of 0-10, with 10 being the worst pain, what is your current level of pain”.
- Research staff will record whether subject had any side effects to report.
- Research staff will collect the subject’s Study Diary.
- Research staff will collect the study pills.
- Subjects will have the following research-driven blood test drawn via 1 venipuncture (5-10 mls, approximately 1-2 teaspoons of blood drawn for each test) which include:
 - Comprehensive metabolic panel (liver function, renal function, plasma glucose tests).
**Subjects who have had a comprehensive metabolic panel test within the one week prior to this visit will not need to have this test repeated unless they are abnormal.*
 - Complete Blood Count.
**Subjects who have had a complete blood count test within the one week prior to this visit will not need to have this test repeated unless they are abnormal.*

Final Visit 5/Week 16:

- Record: Weight (in pounds), blood pressure, history of lower back surgeries, medical history, and concomitant medications.

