- Subjects will be asked to complete the following questionnaires:
 - RMDQ
 - PIQ-6
- Subjects will be asked “On a scale of 0-10, with 10 being the worst pain, what is your current level of pain”.
- Subjects will be asked if they are undergoing any other treatment for back pain, when the last treatment was, and whether or not they were satisfied.
- Subject will be asked if they have taken any medications for pain since their last visit.
- Research staff will record whether subject had any side effects to report.
- Subjects will have the following research-driven blood test drawn via 1 venipuncture (5-10 mls, approximately 1-2 teaspoons of blood drawn for each test) which include:
 - Comprehensive metabolic panel (liver function, renal function, plasma glucose tests).
**Subjects who have had a comprehensive metabolic panel test within the one week prior to this visit will not need to have this test repeated unless they are abnormal.*
 - Complete Blood Count.
**Subjects who have had a complete blood count test within the one week prior to this visit will not need to have this test repeated unless they are abnormal.*

DIRECTIONS FOR TAKING MEASUREMENTS:

Directions for weighing subjects: Have subject remove his/her shoes and empty pockets of any items prior to stepping on the scale. Weight should be recorded to the nearest ½ pound (for example 150.5#).

Directions for taking height: Have subjects remove their shoes before taking their height. Height should be recorded to the nearest 1/2 inch (for example 60.5”).

Directions for taking blood pressure: Have subjects sit for 5 minutes before taking blood pressure.

VISIT WINDOWS: Visits will have a 1 week visit window. If a subject fails to come in within this visit window, they will be instructed to bring in any unused study pills and removed from the study.

ADHERENCE TO STUDY ASSIGNMENTS: Adherence to study medication will be assessed via review of the “Study Medication Diary”. Compliance will be recorded both in paper format and in the electronic data collection tool. If a subject misplaces their Study Medication Diary, they will be asked to reproduce it from memory to the best of their ability. Subjects will be instructed to bring back all of the bottles regardless of whether there are empty or contain missed doses.

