If a subject misses a dose, regardless of the amount, they will be encouraged to document this in their study diary and resume taking their pills. All subjects will remain in the study and continue with all the study related visits.

If a subject misplaces or loses their study medication, they will be instructed to return to the research department and will be given a new bottle of their assigned study medication. Since the research coordinator is not blinded, they will be able to give the medication that the subject was assigned.

If a subject forgets to bring their study medication in for their visit, they will be instructed to bring it in at their earliest convenience.

WITHDRAWAL PROCEDURES: If at any time during the study, the subject decides to withdraw consent or if the subject is withdrawn from the study by the investigator, they will be referred to their Primary Care Manager (PCM) to continue with standard of care treatment.

PREGNANCY: Subjects must agree to take precautions to prevent pregnancy during the course of this study due to the possible effect MSM may cause an unborn child. The only completely reliable methods of birth control are total abstinence or surgical removal of the uterus. Other methods, such as the use of condoms, a diaphragm or cervical cap, birth control pills, IUD, or sperm killing products are not totally effective in preventing pregnancy. In addition, women who are breastfeeding may not participate in this study.

If a subject unintentionally becomes pregnant, they will be instructed to cease taking their study pills, return their pill bottle and will be removed from the study.

DISPOSAL OF STUDY RELATED PILLS: Subjects will return any remaining study-related pills directly to the Research Coordinator or Principal Investigator. The Research Coordinator or Principal Investigator will be responsible for disposing of the study-related pills. The preferred method of disposal is to have the Pharmacy dispose of them. If the Pharmacy is unable to dispose of them, they will provide directions on safe disposal for the Research Coordinator or Principal Investigator to follow.

OTHER: Subjects will take their study pills daily and will be permitted to have the usual medical care for other co-morbid and acute conditions if applicable. Analysis described above using intention-to-treat principles for any missing data will be used (we will use the carry-forward method to impute missing data).

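### Carry-forward is the only missing-data method, with no stated target effect and no sensitivity analysis, and the visit-window rule adds avoidable missing outcomes

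*Combined protocol and SAP*

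**What the plan says.** The missing-data rule is one sentence under OTHER in section 3.6: "intention-to-treat principles for any missing data will be used (we will use the carry-forward method to impute missing data". No section states a missingness assumption or a sensitivity analysis. Section 6.3 plans a mixed effects repeated measures analysis of covariance, and section 6.1 lists weeks 0, 4, 8, 12 and 16. Neither says whether the effect of interest is that of staying on pills or that of assignment whatever happens later. Section 6.4 enrols 100 to obtain 68 completers.

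Three rules in section 3.6 govern who stays under observation:
- VISIT WINDOWS: a subject who misses the one-week window is told that "they will be instructed to bring in any unused study pills and removed from the study".
- WITHDRAWAL PROCEDURES: for subjects who withdraw or are withdrawn, "they will be referred to their Primary Care Manager (PCM) to continue with standard of care treatment". PREGNANCY also ends participation. No section provides for collecting outcomes afterwards.
- ADHERENCE TO STUDY ASSIGNMENTS, on missed doses: "All subjects will remain in the study and continue with all the study related visits".

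On the expected course, section 3.5 (Patient Selection) says that among patients with chronic low back pain "90% endorse stable pain and disability". Section 3.5 (Proposal of Materials and Methods) describes one osteoarthritis trial with more improvement at weeks 8 and 12 than at week 4, "suggesting that improvement in symptoms may require longer exposure MSM". Visit 4/Week 12 is marked "SUBJECTS STOP TAKING STUDY PILLS AT THIS VISIT". The footnote to section 3.6.7 has prior naproxen users scored at Visit 1 after a two-week washout and lets them restart afterwards.

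**The concern.** Carry-forward enters the last observed score at every later visit. That is correct only if a lost subject's score would not have changed. Three features of this plan make that doubtful:
- the plan itself expects the MSM effect to build with exposure;
- a carried baseline score is a post-washout score for prior naproxen users, who may restart naproxen after Visit 1;
- a subject lost after week 12 has an on-pill score entered for the off-pill week 16 visit.

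The direction of the error depends on the target effect. Against the effect of staying on pills, freezing a growing benefit understates it. Against the effect in all randomised subjects, freezing a benefit that fades after removal overstates it. Since the plan does not name the target, a reader could not tell which error applies. The visit-window rule adds to the problem by ending outcome collection for lateness alone, while subjects who miss doses attend every visit.

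**Working it through.** **The plan's own figure.** Loss allowance = (100 − 68)/100 = 32%. This is a planning allowance. Consent and screening precede randomisation at Visit 1, so some of the 32 may be screen failures; equally, nothing prevents higher loss. I therefore also show half of it, 16%.

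**Assumptions (the documents give no SD, loss timing or loss by arm).** The effect grows linearly to 0.50 SD at week 12, so it is 0.167 at week 4 and 0.333 at week 8. Loss is equal in both arms. There are two timings:
- *Spread:* 8% lost in each of the four intervals between visits, so 76% are still observed at week 12.
- *Early:* 10.67% lost in each of the three intervals before week 12, so 68% are still observed.

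**Week 12 at 32% loss.**
- Carry-forward, spread: 0.76 × 0.50 + 0.08 × (0 + 0.167 + 0.333) = 0.42. Early: 0.68 × 0.50 + 0.1067 × 0.50 = 0.393.
- All randomised, removed subjects lose all benefit: 0.76 × 0.50 = 0.38; 0.68 × 0.50 = 0.34.
- All randomised, removed subjects keep half of the benefit at their last visit: 0.38 + 0.02 = 0.40; 0.34 + 0.027 = 0.367.

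| Week 12 effect, SD (spread / early) | 16% loss | 32% loss |
|---|---|---|
| Staying on pills | 0.50 | 0.50 |
| Carry-forward | 0.46 / 0.45 | 0.42 / 0.39 |
| All randomised, half kept | 0.45 / 0.43 | 0.40 / 0.37 |
| All randomised, none kept | 0.44 / 0.42 | 0.38 / 0.34 |

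**On the RMDQ.** Section 3.5 cites authors who "suggest that a 2-3 point difference is a MCID". For a true on-pill benefit of 2 points, multiply by 2/0.50. At 32% loss, carry-forward reports 1.68 / 1.57 points, against 1.52 / 1.36 if all benefit is lost.

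**Week 16, if the effect has gone by then (assumption).** Spread: 0.08 × 0.50 × (0 + 1/3 + 2/3 + 1) = 0.08 SD. Early: 0.1067 × 0.50 × (0 + 1/3 + 2/3) = 0.05 SD. Both are spurious.

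**Scale of the bias.** With 50 per arm, the plan's correlation of 0.8 and baseline adjustment, the standard error is √[2 × (1 − 0.8²)/50] = 0.12 SD. The largest gap above is 0.50 − 0.393 = 0.107 SD.

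**Would the mixed model alone do better?** Without follow-up, a model assuming missing at random returns the on-pill 0.50. That is further from 0.38 or 0.40 than carry-forward's 0.42. If a fraction p of removed subjects is followed, its estimate is close to the mean over those observed:
- All benefit lost: 0.38/(0.76 + 0.24p) = 0.42 gives p = 0.60; early, 0.34/(0.68 + 0.32p) = 0.393 gives p = 0.58.
- Half kept: (0.38 + 0.02p)/(0.76 + 0.24p) = 0.42 gives p = 0.75; early, (0.34 + 0.027p)/(0.68 + 0.32p) = 0.393 gives p = 0.73.

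A simulation of the restricted-maximum-likelihood model agrees for the all-lost case with spread loss: 0.50, 0.43–0.44, 0.42 and 0.375 at 0, 50, 60 and 100% follow-up.

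**Unequal loss (assumed, no true effect).** Let both arms shift by 0.8 SD after baseline, with loss of 42% and 22% spread over four intervals. The arms then differ by 10.5% − 5.5% = 5% in carried baselines, a false 0.05 × 0.8 = 0.04 SD towards either arm.

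**The case against.** The best defence of carry-forward is the plan's statement that chronic low back pain is stable. That supports freezing the underlying pain. It does not support freezing a treatment effect, or a score taken during naproxen washout.

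The second defence is size. Under equal loss the bias is below about one standard error, and simulated type I error stayed at 4–6%. This stands, and it limits the point to interpretation and precision of the estimate.

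Four stronger readings are tempting, and the documents do not support them:
- *The window rule breaks intention-to-treat.* Carry-forward keeps removed subjects in the analysis, and the sentence about remaining in the study belongs to the missed-dose paragraph. What stands is that collection stops for lateness alone.
- *Loss after randomisation is at most, or will be, 32%.* The figure is a planning allowance.
- *Carry-forward invalidates the test or costs power.* Nothing here shows that under equal loss. Unequal loss could bias either way, but the documents do not show it. Section 3.5 reports adverse reactions no more frequent on MSM than on placebo.
- *Dropping carry-forward for the mixed model is enough.* Below the follow-up shares worked out above, it is further from the all-randomised target.

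**Conclusion.** The concern holds, at moderate weight. The plan rests its missing values on a freezing assumption that its own text makes doubtful, does not say which effect it estimates, and tests nothing. That defect needs no assumed number.

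At 32% equal loss, with linear growth to 0.50 SD, carry-forward is 0.08–0.11 SD too low for the on-pill effect. For the all-randomised effect it is 0.02–0.05 SD too high, depending on how much benefit removed subjects keep. These figures depend on the assumed effect shape, loss timing and fading.

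Separately, the visit-window and missed-dose rules treat outcome collection differently without a stated reason and must be reconciled. The naproxen restart in section 3.6.7 and the request in section 4.6 not to resume NSAIDs also need reconciling; that is a separate matter.

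**What to change.** 1. **Analysis (section 3.6, OTHER, and section 6.3).** Delete the carry-forward parenthesis and state: *The target is the difference between arms at each visit in all randomised subjects, whether or not study pills continue. The planned mixed model is fitted by restricted maximum likelihood to all observed visits of all randomised subjects, assuming data missing at random.*
2. **Outcome collection (VISIT WINDOWS, WITHDRAWAL PROCEDURES, PREGNANCY).** Replace the removal wording so far as it ends outcome collection, and state: *Scheduled outcome questionnaires are still collected and analysed for any randomised subject who is late, is withdrawn by the investigator or stops pills, unless consent is withdrawn; late visits are recorded as out of window.* This concerns outcome collection only and changes no rule on pills.
3. **Sensitivity analysis.** Add one multiple-imputation analysis that worsens missing scores by delta, in each arm in turn. Set delta as fractions of the baseline SD, or of the range of the RMDQ version used, and extend it far enough to cover loss of the whole observed benefit. Fixed point values would not do: section 6.1 allows maxima of 11, 18 or 24, so 3 points is 27% of the shortest scale and 12.5% of the longest.

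Parts 2 and 3 are essential to part 1.

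**Cost.** A short amendment and analysis wording, with no extra subjects and no visits beyond the schedule. If all 32 were lost after randomisation and every one could be followed, 8 × (4 + 3 + 2 + 1) = 80 (spread) to 10.67 × (4 + 3 + 2) = 96 (early) of 400 post-baseline visits would be kept. The real gain is smaller, since consent withdrawals cannot be followed and the documents do not say what share of loss the window rule causes. The downsides are staff effort, some off-schedule data, and reliance on missing at random for those not followed.

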3.6.4. Date(s): June 2014-June 2016

3.6.5. Source of Research Material:

Source of Research Material per Participant (Procedures)	# Routine Care	# Research Driven	# Total Procedures
PIQ6	0	5	5
RMDQ	0	5	5
Study Diary	0	5	5

Serum pregnancy test for women of child-bearing potential	0	1	1
Comprehensive metabolic panel	0	5	5
Complete Blood Count	0	5	5

All specimens kept at NELLIS AFB will be handled and disposed of in accordance with federal regulations.

3.6.6. Subjects:

We will recruit male and female NELLIS AFB DoD beneficiaries between the ages of 18-65 years old with symptoms of lower back pain from any of the clinics at the Mike O'Callaghan Military Medical Center at Nellis Air Force Base. Some subjects may be the patients of the PI or AI; however, the PI will have the AI, or Study staffs recruit their patients to prevent any misconception of coercion. No special populations (i.e. children, prisoners, pregnant women, mentally disabled persons, or economically or educationally disadvantaged persons) will be eligible for this study.

3.6.7. Inclusion/Exclusion Criteria:

- **Inclusion:**
 - DoD beneficiaries between the ages of 18-65 years old.
 - Symptoms of Low Back Pain greater than 12 weeks duration.
 - Patients with a history of lower back surgery may be included.
- **Exclusion:**
 - DoD beneficiaries less than 18 years old or greater than 65 years old.
 - Lower back pain caused by any of the following:
 - Infection
 - Tumor
 - Osteoporosis
 - Ankylosing spondylitis
 - Fracture
 - Deformity
 - Inflammatory process
 - Cauda equina syndrome
 - Treated or untreated central nervous system impairment.
 - Meeting the criteria for surgery, including:
 - progressive motor deficit
 - sphincter impairment from neurological cause
 - disabling sciatic pain (in the absence of backache) lasting 6 weeks or more that is attributed to a compromised nerve root and demonstrated by magnetic resonance imaging or computed tomography
 - Oncologic disease during the previous 5 years.
 - Unexplained weight loss, fever, or chills.
 - Diagnosed upper urinary tract infection within last 28 days.
 - Patients identified during standard of care interview to have a history of intravenous drug use.
 - Immunocompromised host.
 - A severe comorbidity to include:
 - a detriment to the subjects overall well-being (e.g. painful disabling arthritic hip joints)
 - Cirrhosis
 - Ongoing dialysis
 - Radiating symptoms to lower extremities (sciatica).
 - History of bleeding disorders.
 - History of high blood pressure.
 - History of heart, kidney, liver or ulcer disease.
 - Allergic to analgesics or Non-steroidal anti-inflammatory agents (NSAIDs).
 - Pregnant or breastfeeding.
 - Initial pain rating of greater than 8/10 on initial intake evaluation
 - If the comprehensive metabolic panel is reviewed by the PI, and any of the values are outside a range deemed safe for the subject to be included in study.
 - If any of these four components of the complete blood count is reviewed by the PI, and any of the values are outside a range deemed safe for the subject to be included in study:
 - White blood cell count
 - Hemoglobin
 - Hematocrit
 - Platelets

- Patients taking any of the following medications are excluded from participating, unless they agree to wash out for two weeks prior to entering the study:
 - Muscle relaxers of any type
 - Tramadol
 - Gabapentin
 - Pregabalin
 - Glucosamine
 - Narcotic pain medications
 - Non-steroidal anti-inflammatory agents (NSAIDs)

* Patients taking naproxen must agree to wash out for two weeks prior to entering the study, but can begin taking it again, as prescribed, after Visit 1 where a baseline pain assessment is performed.

